#### 4 Abbreviations

AE	Adverse Event
AR	Adverse Reaction
CA	Competent Authority
CEC	Clinical Events Committee
CI	Chief Investigator
CKD	Chronic kidney disease
CRF	Case Report Form
CRO	Contract Research Organisation
CTA	Clinical Trials Authorisation
CVD	Cardiovascular Disease
DPP	Diabetes Prevention Programme
DSUR	Development Safety Update Report
DTU	Diabetes Trial Unit
eCRF	Electronic clinical research form
eGFR	Estimated Glomerular Filtration Rate
GP	General Practitioner
GCP	Good Clinical Practice
HDL	High-Density Lipoproteins
HDPE	High-Density Polyethylene
HES	Health Episode Statistics
IB	Investigator Brochure
ICF	Informed Consent Form
IDMC	Independent Data Monitoring Committee
IMP	Investigational Medicinal Product
IRB	Independent Review Board
ISF	Investigator Site File
LDL	Low-Density Lipoproteins
LFTs	Liver Function Tests
MI	Myocardial infarction
MRC	Medical Research Council
MHRA	Medicines and Healthcare products Regulatory Agency
NDH	Non-Diabetic Hyperglycaemia
NIMP	Non Investigational Medicinal Product
NRES	National Research Ethics Service
OC	Operational Committee
OGTT	Oral Glucose Tolerance Test
PI	Principal Investigator
PIC	Participant Information Centre
PIL	Participant Information Leaflet
PSSRU	Personal Social Services Research Unit
R&D	NHS Trust Research and Development Department
RA	Regulatory Agency
REC	Research Ethics Committee
RSI	Reference Safety Information
SAE	Serious Adverse Event
SAR	Serious Adverse Reaction
SDV	Source document verification
SmPC	Summary of Product Characteristics

SOP	Standard Operating Procedures
SUSAR	Suspected Unexpected Serious Adverse Reaction
T2DM	Type 2 Diabetes Mellitus
TMF	Trial Master File
TSC	Trial Steering Committee
UKPDS	UK Prospective Diabetes Study
WHO	World health Organisation

# 5 Trial Synopsis

Title of clinical trial	G lucose Lowering In Non-diabetic hyperglycaemia Trial ( GLINT ) – a randomised controlled trial to establish the effectiveness and cost-effectiveness of metformin in preventing cardiovascular disease (CVD) events over five years in people with non- diabetic hyperglycaemia at high cardiovascular risk
Sponsor name	Cambridge University Hospitals NHS
	Foundation Trust and the University of
	Cambridge
Eudract number for proposed trial	2012-005570-56
Medical condition or disease under investigation	Non-diabetic hyperglycaemia (NDH) (HbA 1c $\geq$ 36.6mmol/mol but <47.5mmol/mol) with an estimated 10-year CVD risk $\geq$ 20% (Framingham/QRISK2)
Purpose of clinical trial	To establish the effectiveness and cost- effectiveness of metformin in preventing cardiovascular events over five years in people with non-diabetic hyperglycaemia at high cardiovascular risk
Primary objective	To evaluate the effect of adding metformin to the usual care of participants with NDH on a composite macrovascular endpoint (cardiovascular mortality, nonfatal myocardial infarction or nonfatal stroke)
Secondary objective (s)	To evaluate the effect of adding metformin to the usual care of participants with NDH on: •Each component of the primary composite endpoint •All-cause mortality •Incidence of non-melanoma cancer •Death due to a non-melanoma cancer cause •Incidence of physician-diagnosed type 2 diabetes •Participant satisfaction with treatment •Functional status •Health utility

	Multi contro, randomicod, doublo blind
Study Design	
	parallel group, pragmatic, primary prevention
	trial comparing the effect of prolonged-
	release metformin with placebo on a
	composite macrovascular outcome in people
	with non-diabatic hyperalycappia (NDH) and
	high CVD risk in primary care
Study Endpoints	Primary Endpoint: Time to first confirmed
	event in the primary composite
	macrovascular endpoint (cardiovascular
	macrovascalar chapoline (caralovascalar mortality, nonfatal myocardial infarction or
	nortality, normatal myocardial infarction of
	nomatal stroke).
	Secondary Endpoints:
	
 
Time from randomisation to the first
 

	confirmed event of the individual
	components of the primary composite
	and point i a cardiovascular mortality
	nonfotol mysecondial information monfotol
	nonialai myöcarulai miarcion, nonialai
	stroke
	
 
Time to any cause of death (supplied by
 

	Office of National Statistics)
	•Time to first non-melanoma cancer
	(supplied by the National Cancer
	Registry)
	• Time to death due to a non-melanoma
	cancer cause according to primary /
	underlying cause of death on death
	certificate (supplied by the Office of
	National Statistics)
	Incident type 2 disbetes mellitus (T2DM)
	•Incluent type 2 diabetes menitus (12DM)
	(physician diagnosed)
	
 
Participant satisfaction with treatment
 

	(adapted DTSQ)
	
 
Functional status (SF-8)
 

	•Health utility (EuroOol ÉO-5D)
	The study will begin with a 250 participant
Sample Size	fassibility phase. The fassibility phase sime to
	reasibility phase. The reasibility phase aims to
	test the practicalities of different aspects of
	the study to confirm that it is possible to use
	this study model. If the analysis of the
	feasibility phase determines that this model is
	viable, the second phase of the study will
	commonico and an additional 12 649
	commence and an additional 12,040
	participants will be recruited; bringing the
	total sample size to 12,898. Analysis of the
	study efficacy will be conducted after 1,046
	confirmed primary composite endpoint events
	have accrued.
	Inclusion critoria:
Summary of eligibility criteria	The basical sector and the sector an
	To be included in the study the participant
	must meet all of the following criteria:
	
 
Understand the study procedures,
 

	alternative treatments available, and

the risks involved with the study and
voluntarily agree to participate by
providing written informed concent
•Age ≥ 40 years
•HbA 1c $\geq$ 36.6mmol/mol but
<47.5mmol/mol; measured within one
year prior to enrolment

 
•Estimated 10-year CVD risk ≥20% as
 

assessed by the Framingham or
QRISK2 scores; laboratory values used
for the risk calculators should be
collected no more than one year prior
to enrolment.
•Estimated glomerular filtration rate
(eGFR) >45ml/min as determined by
the MDRD-4 method: measured within
6 months prior to enrolment
Derticipant agrees to allow study staff to
•railicipant ayrees to anow sludy stall to
and/or consultant to notify them of
and or consultant to notify them of
medical records necessary for
complete data ascertainment during
the follow-up period (including
recording of NHS number and access
to Health Episode Statistics (HES))

 
Participant agrees to be flagged with the
 

Office for National Statistics and the
National Cancer Registry for:

 
Time to first non-melanoma
 

cancer diagnosis (supplied by
National Cancer Registry)
oTime to death due to a non-
melanoma cancer cause
according to primary/underlying
cause of death on death
certificate (supplied by the
Office of National Statistics)
Exclusion criteria:
The participant may not enter the study
if ANY of the following apply:
II ANT OF the following apply.
Onable to provide written consent
Prior history of physician-diagnosed
IZDM.
NOTE: Participants with a history of
gestational diabetes which resolved
after pregnancy are permitted to
enrol.

 
Prior history of CVD, defined as:
 

 
myocardial infarction, surgical
 

or percutaneous coronary
revascularization procedure

 
Stroke (haemorrhagic or
 

	ischaemic)
	NOTE: Participants with prior
	transient ischaemic attack or
	unstable angina are NOT
	excluded and may be enrolled
	Participant has a planned or anticipated
	coronary revascularization procedure
	within 6 months following enrolment
	NOTE: Participants with previous
	norinhoral rovascularisation
	peripheral revascularisation
	procedure are not excluded and
	Darticipant is broastfooding or known to
	Participant is breastreeding of known to
	De pregnant
	Participant is currently taking     mathematic (far any reason) or they have
	metrormin (for any reason) or they have
	taken metformin in the last three
	months
	History of cirrnosis of the liver or other
	significant nepatic impairment, as
	assessed by medical history
	End-stage renal disease (CKD stage 3b)
	or worse, eGFR<45ml/min)
	• In the investigator's opinion,
	participant has a medical history that
	indicates a life expectancy of <2 years
	or might limit the individual's ability to
	take the study treatments for the
	duration of the study.
	
 
Any other significant disease or
 

	disorder which, in the opinion of the
	Investigator, may either put the
	participant at risk because of
	participation in the study, or may
	influence the result of the study, or the
	participant's ability to participate in the
	study.
	Participant is enrolled in or has participated
	within 12 weeks prior to enrolment in another
	experimental protocol involving the use of an
	investigational drug or device or an
	intervention that would interfere with the
	conduct of the study
Investigational medicinal product	Prolonged-release metformin (Glucophage)
and dosage	tablet form 1500mg (3 x 500mg/day).
Comparator product(s)	Placebo tablet
Route(s) of administration	Oral
Maximum duration of treatment	Feasibility phase: Study duration is driven by
of a participant	the time required to recruit and follow 250
	participants for at least a median of 6
	months, anticipated duration is 30 months.
	· ·

	Full study: duration is driven by the time to
	accumulate 1,046 confirmed events in the
	primary composite endpoint, anticipated
	duration is 5-7 years
Procedures:Recruitment	3 recruitment methods:
	
 
NHS Health Checks programme
 

	
 
Existing research databases held by
 

	GLINT investigators
	
 
Search of GP electronic records using risk
 

	scores to identify potential eligible
	individuals
Baseline	•Consent
	
 
Assessment of Eligibility
 

	
 
Blood sample taking
 

	
 
Clinical measures
 

	•Questionnaire
Treatment period	
 
Study medication
 

	
 
Annual questionnaire
 

End of study	
 
End of study questionnaire
 

Procedures for safety monitoring	100% source document verification (SDV) on
during study	first 5 participants at each site; outcome will
5 ,	determine further monitoring frequency. The
	IDMC will also monitor the safety of
	participants during the study
Criteria for withdrawal of	Protocol specified reasons for study
participants on safety grounds	medication discontinuation are:
	An adverse event which requires
	•All duverse event which requires
	modication or recults in inability to
	continue to comply with study
	procedures. Study drug can be
	resumed if the event resolves
	•Development of chronic kidney disease
	(CVD stage 2b or worse
	
 
discontinuation of the study medication or results in inability to continue to comply with study procedures. Study drug can be resumed if the event resolves.
 
Development of chronic kidney disease
 

#### 6 Study Flow Chart

ANNUAL FOLLOW-UP UNTIL END OF STUDY All participants will be sent an annual questionnaire including questions on CVD, cancer and diabetes incidence; adverse events; medication adherence; SF8, EuroQol (EQ5D), treatment satisfaction; health service use in last 12 months; GPs will receive an annual questionnaire regarding vital status; CVD, cancer and diabetes incidence; adverse events; current medication; most recent eGFR value (if present)**	
---	--

\*Note that we do not plan to collect LFTs or B12 at baseline in the full study (following safety results from the feasibility phase); we do not plan to collect creatinine measures during study follow-up, (following safety results from the feasibility phase), although we will ask GPs to supply this value if available \*\* If eGFR < 45ml/min, study medication should be stopped

#### 7 Background and rationale for study

Cardiovascular disease (CVD) is a major UK public health problem associated with substantial premature mortality, morbidity and financial cost (1). In the UK, population screening and risk factor reduction programmes are being implemented (2). High glucose levels are a risk factor for CVD (3). However, considerable uncertainty exists about the appropriate screening and treatment strategies for this risk factor. People with established T2DM are at increased CVD risk, but the degree to which that risk is modulated through glucose control is unclear. Observational studies show a consistent and continuous association between glycaemia and CVD risk, even below the diagnostic threshold for T2DM i.e. non-diabetic hyperglycaemia (NDH) (3-5). Despite this association, interventional trials have not consistently demonstrated reductions in CVD risk with intensive glucose control. The UK Prospective Diabetes Study (UKPDS), conducted in newly diagnosed diabetic patients, showed a reduced risk of myocardial infarction (RR 0.67, 95% CI 0.51 to 0.89) and all-cause mortality (RR 0.73, 95% CI 0.59 to 0.89) with metformin based treatment (6). In contrast, randomised trials of intensive control of hyperglycaemia, mainly involving agents other than metformin, in those with longstanding T2DM, have not demonstrated significant reductions in major cardiovascular event composites (7-9). Meta-analyses pooling all of the glucoselowering trials in people with T2DM suggest a small, but statistically significant beneficial effect of intensive glucose control on CVD endpoints (10, 11). The hypothesis that tight glycaemic control is more important early in the course of T2DM or prior to its development, before macrovascular disease has developed, could unify these findings and is supported by subgroup analyses showing greater CVD effect in those with a shorter duration of T2DM (7-9).

The effect of glucose lowering on CVD mortality and events in people with NDH is unknown. This is an important gap in the current research base (12), particularly at a time when population-based programmes to identify those at high CVD risk are being undertaken. Non-diabetic hyperglycaemia affects 15-20% of the adult population and around 50% of all CVD events attributable to higher than normal glucose levels occur in this group (4). If a cheap and safe drug, such as metformin, were shown to reduce CVD risk, via reductions in glycaemia as well as other mechanisms (13), it would have important population health and economic benefits. There have previously been no primary CVD prevention trials evaluating metformin in people with NDH. The US Diabetes Prevention Programme (DPP) randomised approximately 1000 participants to metformin for diabetes prevention, but is under-powered to examine its impact on CVD events. We plan to quantify the effect of metformin compared to placebo on CVD risk in individuals with NDH using an individually-randomised controlled trial design.

Hyperglycaemia, insulin resistance and obesity are risk factors for malignancy (14). Recent observational data link metformin use to a 37% reduction in incidence of major common cancers, including bowel, lung and breast (15), and this is supported by a body of evidence describing plausible mechanisms of action in addition to glucoselowering (16). Among patients with T2DM use of metformin is associated with a halving of cancer mortality (17). However, these epidemiological data are limited by residual confounding and cannot establish causality. Indeed, a recent meta-analysis does not support the hypothesis that metformin lowers cancer risk by one-third (18). By randomising participants to metformin therapy, our study will also be able to evaluate the potential relationship between metformin and risk of cancer.

Previous T2DM prevention studies (19-25) have identified high risk individuals using an oral glucose tolerance test (OGTT). This method of identifying an at-risk population sub-group is challenging for practitioners and patients alike and is impractical within the context of a population-based CVD risk reduction programme. Our proposed study will assess the effect of metformin on outcomes among a high-risk group defined by a more pragmatic screening strategy utilising a non-fasted blood test (HbA1c). A World Health Organisation (WHO) report endorsing the use of HbA1c as an alternative test to the OGTT for defining T2DM has been published and is likely to impact on UK clinical practice (26). The cut-point for defining among asymptomatic non-pregnant individuals is HbA1c  $\geq$ 47.5mmol/mol (26, 27). The Expert Committee noted that the risk of T2DM and cardiovascular disease was elevated in people with NDH as defined by HbA1c. The risk of progression to T2DM approximately doubles for each 0.5% increase in HbA1c. The American Diabetes Association recommends the range 38.8 to 46.4mmol/mol to define those at high risk but acknowledges that 'the most appropriate level above which to initiate preventive interventions is likely to be somewhere in the range of 36.6-42.1mmol/mol' (27). Rather than define a new HbA1c category equivalent to the OGTTdefined impaired glucose tolerance or impaired fasting glucose, the Expert Committee noted that it would be preferable to define a level of NDH at which the benefits of intervention outweigh the risks. Such an analysis requires long-term trials in people with NDH.

GLINT (Glucose Lowering in Non-diabetic hyperglycaemia Trial) is a pragmatic, placebocontrolled, double blinded trial which seeks to determine the impact of metformin on macrovascular outcomes in people with NDH over a median follow up period of five years. It will be run jointly by the University of Cambridge MRC Epidemiology Unit and the University of Oxford Diabetes Trials Unit (DTU). The study is sponsored by Cambridge University Hospitals NHS Foundation Trust and the University of Cambridge. GLINT is conducted in two phases (i) a feasibility phase and (ii) the extended study. The feasibility phase aims to address practicalities to validate the study model and minimise uncertainty concerning trial parameters, prior to commencement of the full study.

Funding for the feasibility phase, which will be carried out in two UK regions, is provided by the NIHR Health Technology Assessment programme. If successful, this will lead into the full study and recruitment will be expanded to a further six geographical regions in the UK.

The study duration is driven by the time to accumulate 1,046 confirmed events in the primary composite endpoint. Initially, 250 participants will be enrolled in the study. The enrolment of a further 12,648 individuals will depend on the outcome of assessment of data from the initial feasibility phase including demonstration of the feasibility of general practice and participant recruitment, the feasibility of randomisation and distribution of study medication, the acceptability of adverse event reporting and outcome assessment and the safety of metformin and the proposed frequency of monitoring of

renal function and B12 levels. Demonstration of a treatment effect within the limited duration of follow-up in the feasibility phase is not an objective.

## 8 Study Design

#### 8.1 Statement of design

GLINT is a multi-centre, randomised, double-blind, parallel group, pragmatic, primary prevention trial comparing the effect of prolonged release metformin with placebo on a macrovascular composite outcome in people with non-diabetic hyperglycaemia and high CVD risk in primary care.

## 8.2 Number of Centres

GLINT is a multi-centre pragmatic trial that will be conducted in eight regions across the UK.

#### 8.3 Number of Participants

A total of 12,898 eligible individuals will be recruited, 250 in the initial feasibility phase, and a further 12,648 over approximately a two year period. Participants will be randomly allocated to treatment with either metformin prolonged-release tablets or placebo, and followed up for a median of approximately five years. The sample size calculation for the study can be found in section 15.3.

#### 8.4 Study duration

The study will continue until 1,046 adjudicated primary endpoints have been accrued, or until the TSC determine a need to terminate the trial. All participants will receive study medication and annual questionnaires until study close-out. All participants that cease study medication will be followed up, if possible, for the full study period. All participants that withdraw from the study will have their vital status ascertained, if possible, at the end of the study.

#### 8.5 Study objectives

#### 8.5.1 Primary objective

The primary objective is to evaluate the effect of metformin in preventing major macrovascular events in participants with NDH.

Objective: To compare the impact of adding metformin versus placebo to the usual care of participants with NDH on major macrovascular outcomes as measured by the primary composite endpoint of CV mortality, nonfatal myocardial infarction or nonfatal stroke.

Hypothesis: Metformin is superior to placebo with regard to the risk of developing a confirmed event in the primary CVD composite endpoint.

#### 8.5.2 Secondary objectives

The secondary objectives are to evaluate the effect of metformin on:

•Time to event for each component of the primary composite endpoint

- •All-cause mortality
- •Time to non-melanoma cancer
- •Death due to a non-melanoma cancer cause
- •Time to incident physician-diagnosed T2DM
- Participant satisfaction with treatment (adapted DTSQ)
- •Functional status (SF-8)

•Health utility (EuroQol EQ-5D)

## 8.5.3 Exploratory objectives

Additional objectives are to evaluate the effect of metformin treatment on:

•Time to confirmed hospital admission for congestive heart failure

- •Time to confirmed hospitalisation for unstable angina
- Time to confirmed coronary, cerebrovascular or peripheral revascularization (e.g. coronary bypass graft, percutaneous intervention with balloon angioplasty or stent)
- Medical resource utilisation during the trial (e.g. hospitalisations, outpatient physician visits, medication use)

# 8.6 Study endpoints

## 8.6.1 Primary endpoint

Time from randomisation to the first confirmed CV event in the primary composite endpoint (CV mortality, nonfatal myocardial infarction or nonfatal stroke).

## 8.6.2 Secondary endpoint

- Time from randomisation to the first confirmed event of the individual components of the primary composite endpoint *i.e.* CV mortality, nonfatal myocardial infarction or nonfatal stroke.
- Time to any cause of death (supplied by Office of National Statistics)
- Time to first non-melanoma cancer diagnosis (supplied by National Cancer Registry)
- Time to death due to a non-melanoma cancer cause according to primary / underlying cause of death on death certificate (supplied by the Office of National Statistics)
- Physician diagnosed T2DM
- Participant satisfaction with treatment (adapted DTSQ) annually from randomisation and additionally at four months post-randomisation in the feasibility phase.
- Functional status (SF-8) annually from randomisation and additionally at four months post-randomisation in the feasibility phase.
- Health utility (EuroQol EQ-5D) annually from randomisation and additionally at four months post-randomisation in the feasibility phase.

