# 24.2 Appendix 2 Modified Safety Reporting

All SAEs listed below are exempted from routine SAE reporting. However they will be assessed for relatedness to the study drug and if the event is considered related and not expected *i.e.* it is a SUSAR it will be reported in an expedited manner.

All SAEs not listed below will be reported as per standard guidelines and processes. In addition a quarterly line listing of these SAEs will be submitted to the sponsor.

1. Primary and secondary study endpoints

These events will prompt the investigator to complete an endpoint package which will then be adjudicated according to the Clinical Events Classification (CEC) charter:

-Cardiovascular (CV) death e.g. fatal myocardial infarction [MI]/cerebrovascular accident [CVA]/ congestive heart failure [CHF]/arrhythmia, cardiac arrest, death following CV intervention

-Non-fatal MI

-Acute coronary syndrome

-Non-fatal CVA

-CHF requiring hospitalization

-Unstable angina requiring hospitalization

-All cause mortality

2.Other Cardiovascular Events of Interest

-Atrial fibrillation/Atrial flutter

-Ventricular fibrillation/tachycardia requiring intervention

-Deep Vein Thrombosis (DVT)

-Pulmonary embolism

-Percutaneous Coronary Intervention (PCI) – (including non-serious events)

-Coronary Artery Bypass Graft (CABG)

-Coronary catheterization

-Stress test (including non-serious events)

-Abdominal aortic aneurysm/repair

-Carotid endarterectomy/ carotid angioplasty and/or stenting

- Any hospitalization due to cardiovascular events (i.e., whether or not the hospitalisation was for an obvious study endpoint)

-Shock/hypotension

-Accelerated or malignant hypertension/hypertensive urgency

-Transient Ischemic Attack (TIA)

-Syncope

-Renal artery angioplasty and/or stenting

-Other arterial angioplasty and/or stenting

3.Non-cardiovascular events of interest

Any non-melanoma incident cancer

Any non-melanoma recurrent cancer

Death due to cancer (any non-melanoma type) Physician diagnosed T2DM

4.Known adverse reactions of metformin

-GI upset / diarrhoea

-Hypoglycaemia

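### The cancer endpoints, as worded, drop melanoma and count non-melanoma skin cancers, which would attenuate the incidence hazard ratio

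*Protocol*

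**What the plan says.** The same restriction appears wherever cancer is an outcome:

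- Synopsis (section 5), secondary objectives: "Incidence of non-melanoma cancer". The synopsis repeats the term in its endpoints and eligibility criteria.
- Section 8.5.2: "Time to non-melanoma cancer".
- Section 8.6.2, incidence: "Time to first non-melanoma cancer diagnosis (supplied by National Cancer Registry").
- Section 8.6.2, mortality: "Time to death due to a non-melanoma cancer cause according to primary / underlying cause of death on death certificate", supplied by the national statistics office.
- Section 9.1: agreement to tagging for these two outcomes is an inclusion criterion.
- Appendix 2 (24.2), events exempt from routine SAE reporting: "Any non-melanoma incident cancer" and "Death due to cancer (any non-melanoma type").

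The protocol never mentions skin cancer and gives no code list for cancer. Section 7 states the purpose broadly: "our study will also be able to evaluate the potential relationship between metformin and risk of cancer". The motivating evidence there concerns "major common cancers, including bowel, lung and breast" and cancer mortality. Section 15.1 has secondary endpoints reported as hazard ratios with 95% confidence intervals and without p-values.

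**The concern.** A common exclusion in cancer endpoints is non-melanoma *skin* cancer. The protocol's term lacks that one word, and without it the meaning turns round: melanoma goes out, and non-melanoma skin tumours come in. It may be a truncated phrase, but the protocol does not say so.

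Two things are at stake.

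- **Incidence.** The endpoint is time to first event. A skin tumour would count as the event, and a later bowel or lung cancer in the same participant would not enter the incidence analysis. If metformin has no effect on skin tumours, the hazard ratio is diluted. With no p-value planned, that ratio and its interval are the whole result.
- **Melanoma.** A potentially fatal malignancy would be missing from both cancer endpoints, without explanation.

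**Working it through.** **Which reading the text supports.** The Appendix 2 entry for cancer death refers to any type that is not melanoma. That phrasing means all cancers except melanoma and does not fit a skin-only exclusion. No other section narrows it.

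**Whether a later step would correct it.** Sections 13 and 17.4 list what the Clinical Events Committee adjudicates: the primary composite, all-cause mortality, heart failure and unstable angina admissions, and revascularisations. Cancer is not listed. Incidence comes from the registry and cancer death from the certificate, so the endpoint wording determines which events count.

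**The protocol's own figure.** The protocol gives no event count or power for cancer. The only related figure is the primary target of 1,046 events (section 15.3: 17% relative risk reduction, 85% power; section 15.1: two-sided 5%). With 1:1 allocation and hazard ratio 0.83:

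- Schoenfeld: 4(1.960 + 1.036)² / (ln 0.83)² gives 1,035 events.
- Freedman: (1.960 + 1.036)² × (1.83 / 0.17)² gives 1,041 events.

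Both are within about 1% of 1,046. The target rests on cardiovascular events alone and does not change.

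**Dilution of the incidence hazard ratio.** Inputs:

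- True hazard ratio for all other counted cancers: 0.63, from the 37% observational reduction cited in section 7.
- Hazard ratio for non-melanoma skin cancer: 1 (assumption).
- f, the share of control-arm first events that are non-melanoma skin cancers: not in the protocol; 10 to 40% assumed.

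If the control-arm event rate is λ, the metformin-arm rate is fλ + (1 − f)λ × HR. Dividing by λ:

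observed HR = f + (1 − f) × HR

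- f = 0.10: 0.10 + 0.90 × 0.63 = 0.667
- f = 0.20: 0.20 + 0.80 × 0.63 = 0.704
- f = 0.40: 0.40 + 0.60 × 0.63 = 0.778

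As a yardstick for lost information, the third column gives the events needed for 85% power at two-sided 5% (Schoenfeld). The last two fix follow-up where the undiluted endpoint yields 169 events and add the skin tumours to both arms. Power is Φ(√d × |ln HR| / 2 − 1.96), with d the total events.

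| f | Observed HR | Events for 85% power | Events at fixed follow-up | Power |
|---|---|---|---|---|
| 0 | 0.63 | 169 | 169 | 85% |
| 0.10 | 0.67 | 219 | 192 | 80% |
| 0.20 | 0.70 | 292 | 221 | 74% |
| 0.40 | 0.78 | 570 | 307 | 60% |

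**Sensitivity to the effect size.** The shift is f × (1 − HR), so a smaller true effect moves less. With a true hazard ratio of 0.80, shares of 20 and 40% give 0.84 and 0.88, shifts of 0.04 and 0.08. With 0.63 the same shares shift it by 0.07 and 0.15.

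**The case against.** - **The trial still answers its question.** A reader might infer that this wording leaves the cancer question unanswered. The documents do not support that. Bowel, lung, breast and every other non-melanoma cancer count, and both arms share one definition. This objection stands: the harm is attenuation plus missing melanoma events.
- **The extract may be right even if the wording is not.** A reader might also infer that the registry will return the wrong events. No extract specification is shown, and a code list may sit in the SAP. It is also unknown whether the registry would supply basal and squamous cell tumours; if it did not, f would be near 0 and only the melanoma loss would remain. This stands as a limit on size. It does not excuse the text: the definition is fixed in the protocol, and a SAP that replaced it would contradict it. The endpoint manual in section 13 is written for the events committee, which does not adjudicate cancer.
- **The magnitude is assumed.** It is. The share f has no source in the protocol, and section 7 itself cites a meta-analysis that does not support a one-third reduction in cancer risk.
- **The reach is limited.** Cancer is a secondary outcome without p-values or a power claim. A fatal cancer after a skin tumour still counts as a cancer death, and melanoma deaths still count in all-cause mortality. Serious melanoma is not lost to safety reporting, since Appendix 2 sends unlisted SAEs through the standard route. All of this stands.

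**Conclusion.** The point holds as a defect of definition with a moderate consequence. As written, and consistently across the protocol, melanoma is excluded from cancer incidence and cancer death, and non-melanoma skin cancers are counted, with no rationale and out of line with section 7.

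If the wording is followed, a true incidence hazard ratio of 0.63 would appear as about 0.67 to 0.78. This assumes that skin tumours make up 10 to 40% of control-arm first events and that metformin does not affect them; neither assumption can be checked in the protocol. The number of melanoma events lost cannot be estimated from it either. The effect on cancer death is probably smaller, which is a judgement, as the protocol gives no figures. The primary endpoint and its 1,046-event target are untouched.

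**What to change.** Before unblinding, redefine the incidence endpoint as time to first malignant cancer excluding non-melanoma skin cancer (ICD-10 C00-C97 except C44, melanoma included), and the mortality endpoint as death from any such cancer. Use identical words in the synopsis, 8.5.2, 8.6.2, 9.1 and the registry extract specification; leaving out the synopsis would create a contradiction that the protocol does not now have. If excluding melanoma was deliberate, the protocol should give the reason.

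Check that consent to tagging covers melanoma. Section 18.1 describes use of cancer registry data without restriction by type, but section 9.1 words the tagging agreement around the restricted term.

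Reconcile Appendix 2 as a separate decision. At present serious non-melanoma cancers, skin tumours included, are exempt from routine SAE reporting and serious melanoma is not. Carrying the new words across would reverse this for both melanoma and non-melanoma skin cancer, so it should not happen as a side effect of an endpoint edit.

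The cost is a protocol amendment to wording, an extract specification, a consent check and the decision on Appendix 2. No sample size, visit or analysis method changes.
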